Participants will be recruited from two VA medical centers, Bedford and Boston VA. Analyses will be conducted at Bedford ENRM VA Hospital.

Study Related Procedures

We will conduct a small-scale experiment using the sites of the CHOIR center (Bedford/Boston). Participants will be identified who:

- Are current VA Bedford or VA Boston patients (including CBOC patients)
- Have uncontrolled diabetes ($HbA1C \geq 8.5$)
- Are inactive users (registered but with at least 1 year of non-use) or non-users of My HealthVet
- Have an upcoming health visit scheduled at Bedford VA or Boston VA.
- Are age 18-85 years old at approximate time of first mailing

CPRS/VistA chart review and administrative data extraction (VSSC files and CDW tables) will be used to identify potential participants and to identify mailing addresses for the patients to be invited to participate Aim 3. As of March 2019, there were 170 eligible patients in Bedford and 539 eligible patients in Boston. (We expect these numbers to shift slightly as new appointments are made or diabetes control changes among the populations.).

All Veterans selected to participate based on these criteria will be sent a mailing including a brochure with information on My HealthVet, a welcome letter introducing the study, an information sheet (modified consent form), and an opt-out card.

All eligible Bedford patients will be invited to participate in a first round of mailings. Based on the opt-out rate of Bedford patients, subsequent round(s) of mailings will be sent to Boston patients in order to have at least 50 patients enrolled in each encouragement arm and at least 50 patients enrolled in the comparison arm (see information about arms in following paragraphs; 200-300 maximum overall across sites).

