Analysis Plan. For this small-scale experiment, we will focus our primary analyses on measuring the effect of the randomized encouragement design on the key proximal process measure of using MHV. We will measure MHV use, including the variety of features (SM, Rx Refills, EHR-extracts (Blue Button, lab views), and frequency of feature use. Because we are interested in the effect of the intervention in the sample targeted, we will conduct an intent-to-treat analysis based on randomization arm regardless of participation in intervention components. As many in the encouragement arm will not participate, this ITT does not directly assess the intervention-attributable effect. Thus, in addition to ITT, we will utilize a complier average causal effect (CACE) analysis to estimate intervention effects for those who engaged with the intervention. CACE estimation makes it possible to estimate the intervention effect for only those who engage. The CACE estimation considers both random assignment and receipt of treatment to estimate intervention efficacy. CACE estimations have been published using instrumental variables, expectation-maximization algorithm, maximum-likelihood, and integrated methods. CACE seeks to compare outcomes for individuals in the intervention condition with those who would have complied with treatment given the opportunity to do so and can often be used to improve power over ITT methods. Like all instrumental-variable methods, CACE estimation requires that certain assumptions be met: that randomization has a causal effect on the exposure (relevance assumption), that the randomization affects the outcome only through the exposure (exclusion restriction), and that randomization and the outcome (MHV use) don't share a common cause (exchangeability assumption). If these assumptions are violated or the instrument is weak, we will fall back on an ITT analysis, using the chi-square test as the statistical test to determine the effect of receiving encouragement on MHV use.

Power: Below, we provide power for ITT analyses, and anticipate additional power when implementing the CACE. We will have power to detect reasonable differences in use of MHV. We have used pilot data, looking at Veterans who did not use the patient portal in 2013 and

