their use patterns in 2014 to estimate behavior in the control. Among diabetics who did not use MHV in 2013, 98% were still not using in 2014, 1% were using at least one feature, and 1% were using more than one feature. A priori estimates are that 30% of Veterans will comply with the encouragement they are randomized to, and among those, 50% will use MHV at least once. With these assumptions, we have 80% power (alpha 0.05) to detect a difference in Intent-to-Treat analysis with a sample of 70 per arm. Although we do not know the exact number who will comply or will go on to use the system, we feel that it is reasonable that half of those who receive the encouragement will begin to use.

8. Ethical Issues

a. Risks

The risks of the study are minimal in that the probability and magnitude of harm or discomfort anticipated in the research are not greater in and of themselves than those ordinarily encountered in daily life or during the performance of routine physical or psychological examinations or tests. Participants will be asked about their diabetes management and how they use My HealthVet.

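### The extra power expected from the CACE analysis is unsupported; power should be claimed for the ITT comparison only unless a specific CACE test is named and simulated

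*Combined protocol and SAP*

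**What the plan says.** The point lies in two paragraphs of Section 7, Planned Statistical Analyses.

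- **Analysis Plan.** ITT is planned first and CACE is added to it. CACE is said to be a method that "can often be used to improve power over ITT methods". The estimator is left open: "CACE estimations have been published using instrumental variables, expectation-maximization algorithm, maximum-likelihood, and integrated methods". The exclusion restriction is listed among the required assumptions. If the assumptions fail or the instrument is weak, the plan reverts to ITT, "using the chi-square test as the statistical test to determine the effect of receiving encouragement on MHV use".
- **Power.** This paragraph opens with the statement at issue: "Below, we provide power for ITT analyses, and anticipate additional power when implementing the CACE". The only figure given is for ITT: "we have 80% power (alpha 0.05) to detect a difference in Intent-to-Treat analysis with a sample of 70 per arm". Its inputs are background use ("98% were still not using in 2014, 1% were using at least one feature, and 1% were using more than one feature") and uptake ("30% of Veterans will comply with the encouragement they are randomized to, and among those, 50% will use MHV at least once").

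Section 4 sets the enrolment floor: "in order to have at least 50 patients enrolled in each encouragement arm and at least 50 patients enrolled in the comparison arm". It also keeps the training guide from the comparison arm until the intervention has ended.

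**The concern.** The plan states a power property as something to be expected, without a calculation or a named test. The CACE effect is larger than the ITT effect, which can look like an easier target, but its standard error grows by the same factor.

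Two things are at stake. First, readers may credit the trial with power beyond the ITT figure. Second, with no CACE test named and no rule for which result governs, a significant CACE could stand beside a non-significant ITT chi-square. The chosen CACE standard error would then decide the conclusion.

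**Working it through.** **Inputs.** From Section 7: comparison-arm use 1% + 1% = 2%; encouragement-arm use 30% × 50% = 15%; alpha 0.05; 70 per arm. From Section 4: at least 50 per arm. Assumed: two-sided alpha, and one encouragement arm against the comparison arm at 1:1.

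**1. The plan's ITT figure.** With mean rate 0.085,

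n = [1.96·√(2·0.085·0.915) + 0.842·√(0.02·0.98 + 0.15·0.85)]² / 0.13² = 71.1, so 72 per arm.

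Power by the same approximation is 79.4% at 70 per arm, so the plan's figure is reproduced. It is 64.9% at 50 and 82.1% at 75.

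**2. CACE on the same inputs.** The comparison arm has no access to the guide or training during the trial. Under the exclusion restriction, CACE = ITT effect / engagement rate, so CACE = 0 exactly when the ITT effect is 0. At 70 per arm:

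- ITT: effect 0.13; SE = √[(0.02·0.98 + 0.15·0.85)/70] = 0.0458; z = 2.84.
- CACE, engagement treated as fixed at 0.30: effect 0.13/0.30 = 0.433; SE 0.0458/0.30 = 0.153; z = 2.84.

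An Anderson-Rubin test of CACE = 0 is the ITT test itself.

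**3. Likelihood-ratio test.** The binary engager/non-engager model was fitted to 600 simulated trials (70 per arm, 2% use among non-engagers, no covariates). The CACE statistic never exceeded the ITT statistic. Rejection was 91.3% for both.

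**4. 2SLS Wald test.** The estimate is d/a, where d is the difference in use and a the observed engagement. The robust SE is √(Σr²)/(n·a), where r is the residual from the comparison-arm rate plus d/a for those who engaged. Each scenario used 300,000 to 400,000 simulated trials. To obtain 2% v 15% under the exclusion restriction, non-engagers never use, and engagers use at 0.02/0.30 = 6.7% untreated and 50% treated.

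| Per arm | ITT chi-square | ITT Wald | 2SLS Wald |
|---|---|---|---|
| 50 | 69% | 74% | 81% |
| 70 | 85% | 87% | 90% |

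(Simulated chi-square power is a few points above the normal approximation in step 1.) Part of the gap is Wald against Pearson standard errors. At 50 per arm, about 12.5% of trials gave a significant CACE beside a non-significant chi-square; at 70 per arm, about 5%.

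**5. Type I error of that test.** Take 9% use in both arms, with engagement tied to use as at the planning values. If non-engagers use at 2%, encouragement-arm use is 0.15 + 0.70·0.02 = 16.4%. Then 0.15/0.164 = 91.5% of users and 0.15/0.836 = 17.9% of non-users engage. At 9% use, engagement is 0.09·0.915 + 0.91·0.179 = 24.6%. At 50 per arm the 2SLS test errs 4.8% in the upper tail and 0.6% in the lower; chi-square errs about 2.5% and 2.4%. At 70 per arm the 2SLS upper tail is 4.2%.

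Allowing chi-square the same upper-tail error as 2SLS, at 2% v 16.4%, gives power of 84.5% v 84.3% at 50 per arm and 93.2% v 93.2% at 70.

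**6. Opposite selection.** Let non-engagers use at 40%, untreated engagers at 10% and treated engagers at 40%, with 30% engagement and 70 per arm. Power in the favourable direction is then 16.9% for 2SLS v 19.7% for chi-square.

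**The case against.** A shared null does not imply equal power for every procedure, and this stands. A reader might infer that the plan's statement is false for any CACE method and that the trial can have only its ITT power. The documents do not support that, because they leave the estimator open and also measure variety and frequency of use. Modelling who engages can help. With two equal strata engaging at 55% and 5% (assumed values, with the weights set to the true rates), an engagement-weighted contrast reached 84% power v 76.5% for chi-square at 50 per arm, with no higher null error. With 45% and 15% the gain was about 2 points, and zero at 70 per arm. Such gains depend on covariates that the plan does not specify.

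It is also fair that the total two-sided error of the 2SLS test in step 5 is near nominal: 5.4% with the robust SE, 5.1% with the classical one. Matching one tail is a reviewer's criterion and not the plan's. That null is also remote from the planning values, since about a third of engagers would use the portal with no intervention effect. At 2% use in both arms and 50 per arm, both tests are conservative, with total error about 1% for 2SLS and 1.3% for chi-square. The tail shift is therefore a scenario result and not a general property.

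Finally, a reader might infer that the expected gain is being used to justify 50 per arm, or that a CACE result would override ITT. Neither is stated. The 80% figure rests on ITT at 70 per arm, the enrolment floor is set without mention of CACE, and CACE is an addition to ITT. The gap between 50 and 70 is a separate matter.

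**Conclusion.** The concern holds in limited form: the expected gain is unsupported, but it has not been shown to be impossible. For the binary comparison without covariates, the gain is zero for the Anderson-Rubin test and was zero for the likelihood-ratio test in simulation. A 2SLS Wald test gains about 12 points at 50 per arm and 5 at 70 under the plan's values. That gain comes partly from its standard error and from a shift of error between tails, and its sign depends on who engages, which is unknown at planning. The power that can be claimed is the ITT power: 79.4% at 70 per arm and 64.9% at 50 by the usual approximation (85% and 69% in simulation).

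This rests on two-sided alpha, no exposure in the comparison arm, the exclusion restriction, and pairwise 1:1 comparisons. If the three encouragement arms were pooled against 50 controls, which the plan does not state, ITT power would be about 78%.

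**What to change.** In Section 7:

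1. Under Power, keep the first clause of "Below, we provide power for ITT analyses, and anticipate additional power when implementing the CACE" and delete the rest. Under Analysis Plan, delete the statement that CACE "can often be used to improve power over ITT methods".
2. State that the trial's power is its ITT power. If a CACE power claim is wanted, name the test and any covariates, and report its simulated size and power under more than one pattern of engagement.
3. State that CACE is a secondary estimate of effect size among those who engage, and that the test of no effect is the ITT test. Give CACE an ITT-consistent interval, for example Anderson-Rubin (Fieller), so that the two results cannot disagree.

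The cost is a few sentences and a different interval formula. Sample size and the ITT analysis are unchanged. The plan loses a power margin that it never quantified.

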If the potential participant does not wish to participate, they can contact study staff by telephone at the number listed on the letter introducing the study. They can also mail the opt-out postcard in order to be removed from contact lists. Potential participants who do NOT indicate that they wish to opt out of future communication from the team within approximately 10 business days of the mailing will be assumed to be enrolled in the study, unless we hear from them to opt-out at a later time. If participants opt out after randomization, we will no longer contact them for other portions of the study. However, we will look at data that we already have for these participants from Aim 1. Those receiving the information sheet (modified consent form) will be informed of the general nature of the study, what their involvement entails, the risk/benefits, and a description of confidentiality. Participants will be told that participation is voluntary, that they can withdraw at any time, and that this will not impact their treatment.

Consistent with the adaptability of a randomized encouragement design, those that do not opt-out will be divided randomly into 4 arms, with at least 50 Veterans in the encouragement arms and at least 50 participants in the comparison arm. Bedford and Boston participants will have separate randomization blocks.

- 1) Comparison arm: My HealthVet brochure only
- 2) Encouragement arm 1: My HealthVet brochure and training guide
- 3) Encouragement arm 2: My HealthVet brochure and training guide plus offering a group training
- 4) Encouragement arm 3: My HealthVet brochure and training guide plus offering a group training and a one-on-one session

All participants in encouragement arms 1-3 will be mailed a paper copy of a training guide. This guide was developed as part of this study based on findings from Aims 1 and 2 and Veteran co-investigator input and does not exist anywhere else. It cannot be posted on a publicly accessible website as this would threaten randomization.

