This aim builds on prior study aims and involves the refinement and pilot testing of an intervention. Using a randomized encouragement design, we will randomize 200-300 Veterans ages 18-85 years old from the Bedford/Boston VAMCs with uncontrolled diabetes ($HbA1c > 8.5$) and no or minimal prior history of using the key MHV features to receive an invitation to one of the following groups, after they have been mailed a brochure and have had the opportunity to opt out of the study. We will aim for each encouragement arm to have at least 50 Veterans, and for the comparison arm to have 50+ enrolled Veterans.

- 1) Comparison arm: My HealtheVet brochure only
- 2) Encouragement arm 1: My HealtheVet brochure and training guide
- 3) Encouragement arm 2: My HealtheVet brochure and training guide plus offering a group training

- 4) Encouragement arm 3: My HealtheVet brochure and training guide plus offering a group training and a one-on-one session

We estimate that 15 to 25 (30-50 percent) of those randomized to each of the 3 encouragement arms will choose to participate by using the training guide or attending a group training or one-on-one session. Feedback on the intervention and patients' intent to use MHV will be gathered from the patient at the one-on-one meeting, the group session, and during their phone interview.

a. Subject Inclusion Criteria

Our primary inclusion criteria are that Veterans:

- Are current VA Bedford or VA Boston patients (including CBOC patients)
- Have uncontrolled diabetes ($HbA1C \geq 8.5$ at last test)
- Are inactive users (registered but with at least 1 year of non-use) or non-users of My HealtheVet
- Have an upcoming health visit scheduled at Bedford VA or Boston VA.
- Are age 18-85 years old at approximate time of first mailing

b. Subject Exclusion Criteria

Veterans are excluded if they do not meet the above criteria (e.g., they are already active MHV users, their most recent HbA1c at the time of recruitment was $< 8.5\%$, or they are age 86 and over at the time of the initial mailing).

c. Recruitment

Subject Identification and Pre-Enrollment Screening:

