Local Veterans from the Bedford/Boston VA healthcare systems ages 18-85 years old with uncontrolled glucose ($A1c > 8.5$) who have not used the patient portal or have only minimally used it in the past (and have had no use in at least the past 12 months), will be recruited for the study. Based on data from March 2019, we estimate this sample to be 170 eligible Veterans in Bedford and 539 eligible Veterans in Boston. We will mail the My HealtheVet brochure, welcome letter, information sheet, and an opt-out card with prepaid postage to all Bedford Veterans who meet eligibility criteria. All those that do not opt-out within 10 business days by telephoning or returning the opt-out card will be considered enrolled, and will be randomized to one of four arms:

- 1) Comparison arm: My HealtheVet brochure only
- 2) Encouragement arm 1: My HealtheVet brochure and training guide
- 3) Encouragement arm 2: My HealtheVet brochure and training guide plus offering a group training for how to use key My HealtheVet features

- 4) Encouragement arm 3: My HealtheVet brochure and training guide plus offering a group training and a one-on-one session

Based on the opt-out rate of Bedford patients, subsequent round(s) of mailings will be sent to Boston patients in order to have at least 50 patients enrolled in each encouragement arm and at least 50 patients enrolled in the comparison arm and a total of 200-300 total enrolled across both sites.

HIPAA Authorization for Recruitment and/or Screening:

A HIPAA waiver of authorization is required. It is necessary to obtain HIPAA identifiers (e.g., contact information and study eligibility) to contact participants for recruitment purposes.

Consent for Recruitment and/or Screening:

We have requested a waiver of consent for recruitment and/or screening. To help identify potential eligible participants (e.g., study eligibility, contact information), it will be necessary for us to obtain a waiver of consent for recruitment purposes.

Enrollment:

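### The only stated power, 80% for the ITT analysis, assumes 70 per arm, but enrolment aims for at least 50; on the plan's inputs one arm versus comparison then has 65% power (exact 69%)

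*Combined protocol and SAP*

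**What the plan says.** The Power paragraph of Section 7 states one figure: "we have 80% power (alpha 0.05) to detect a difference in Intent-to-Treat analysis with a sample of 70 per arm". Over four arms that is 280 participants. The inputs given there are 98% continued non-use among earlier non-users, 30% engagement with the encouragement, and 50% use among those who engage.

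The enrolment rule uses a different number:
- Section 4: "subsequent round(s) of mailings will be sent to Boston patients in order to have at least 50 patients enrolled in each encouragement arm", with the same minimum for comparison. Randomization is then described "with at least 50 Veterans in the encouragement arms and at least 50 participants in the comparison arm".
- Section 5, Sample Description: "We will aim for each encouragement arm to have at least 50 Veterans, and for the comparison arm to have 50+ enrolled Veterans". The engagement forecast there, "We estimate that 15 to 25 (30-50 percent) of those randomized to each of the 3 encouragement arms", is worked out on arms of 50.
- Section 5c, Recruitment: "at least 50 patients enrolled in the comparison arm and a total of 200-300 total enrolled across both sites".

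Section 7 (Analysis Plan) makes portal use the focus of the primary analyses and says "we will conduct an intent-to-treat analysis based on randomization arm regardless of participation in intervention components". The chi-square test is named there for the ITT fallback. Neither the Analysis Plan nor the Power paragraph says whether the test compares each arm with comparison, all four arms at once, or all encouraged participants with comparison.

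**The concern.** The power figure and the enrolment rule were not reconciled. Boston mailings are sized to reach 50 per arm, so the trial can follow its rule exactly, stop at 200, and never have the power it states. A null arm-level or four-arm result at that size would be read against 80%. The chance of missing the planned effect would in fact be about 31-35% for one arm against comparison, or 40% for a four-arm test. Because the contrast is not named, a reader also cannot tell which result the 80% applies to.

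**Working it through.** **Inputs.** From Section 7 (Power): comparison-arm use p0 = 1 - 0.98 = 0.02; encouragement-arm use p1 = 0.30 x 0.50 = 0.15; alpha 0.05. From Sections 4 and 5: at least 50 per arm and 200-300 in total, so 200/4 = 50 to 300/4 = 75 per arm if the arms are equal. Assumed, because the plan is silent: two-sided test, equal allocation, no multiplicity adjustment, no use among non-engagers, no loss of outcome data.

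**Formula (normal approximation, pooled null variance).** Power = Phi[(|p1 - p0| - 1.96 x SE0) / SE1]. For two arms of n, SE0 = sqrt(2 x pbar x (1 - pbar) / n) with pbar = 0.085, and SE1 = sqrt((0.02 x 0.98 + 0.15 x 0.85) / n).

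**The plan's own figure, n = 70.** SE0 = sqrt(0.15555/70) = 0.0471 and SE1 = sqrt(0.1471/70) = 0.0458. The argument is (0.13 - 0.0924)/0.0458 = 0.82, so power is 79.4%. The stated 80% reproduces.

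**At the enrolment floor, n = 50.** SE0 = 0.0558 and SE1 = 0.0542. The argument is (0.13 - 0.1093)/0.0542 = 0.38, so power is 64.9%.

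**Pooled encouragement against comparison, 150 vs 50.** pbar = (50 x 0.02 + 150 x 0.15)/200 = 0.1175. SE0 = sqrt(0.1175 x 0.8825 x (1/50 + 1/150)) = 0.0526 and SE1 = sqrt(0.0196/50 + 0.1275/150) = 0.0352. The argument is 0.76, so power is 77.8%.

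**All contrasts.** Exact means the rejection probability of the uncorrected Pearson chi-square, by enumerating both binomials. The four-arm test is the 3-df Pearson chi-square, simulated.

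| Contrast | 50 per arm | 70 per arm | 75 per arm |
|---|---|---|---|
| One arm vs comparison, normal | 65% | 79% | 82% |
| One arm vs comparison, exact | 69% | 85% | 88% |
| Four arms, simulated | 60% | 81% | 85% |
| Pooled vs comparison, normal | 78% | 93% | 94% |
| Pooled vs comparison, exact | 83% | 95% | 96% |

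At 70 per arm, the 80% fits one arm against comparison or the four-arm test. It does not fit 210 vs 70.

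**Size needed for 80%.** One arm vs comparison: 72 per arm (4 x 72 = 288) by normal approximation, or 63 (4 x 63 = 252) exact. Four-arm test: about 69 (4 x 69 = 276).

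**Sensitivity at 50 per arm.**
- If non-engagers use the portal at the 2% background rate, p1 = 0.15 + 0.70 x 0.02 = 0.164. Power is 71% (exact 76%) for one arm, 69% for four arms and 85% (exact 89%) pooled.
- With 40% engagement, p1 = 0.40 x 0.50 = 0.20. Power is 83% (exact 89%) for one arm and 87% for four arms.
- One arm reaches 80% when use is 19.0% (normal) or 17.4% (exact), that is engagement of 0.190/0.50 = 38% or 0.174/0.50 = 35%.
- With Fisher's exact test, one-arm power is 51% at 50 and 74% at 70 per arm.

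**The case against.** The best case for the plan has five parts.

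1. The stated figure is correct for the size it names, and 280 lies inside 200-300. Fifty is a floor, not a cap. Section 4 notes that "there were 170 eligible patients in Bedford and 539 eligible patients in Boston", so 280 is 280/709 = 39.5% of the pool, and enrolment is by opt-out. This stands: the shortfall is possible, not inevitable, and the point is one of consistency rather than a miscalculation.

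2. The hypothesis in Section 3 and parts of Section 7 speak of a single encouragement arm, which suggests encouraged versus not encouraged. On that reading the floor gives 78% (exact 83%), close to the stated figure, and 53 per arm gives 81% by normal approximation. A paragraph written for a two-group trial of 70 vs 70 would also yield 79%, so the match does not prove that a pairwise test within four arms was meant. This also stands, but Section 7 defines ITT by randomization arm as well. The ambiguity is a reason to name the contrast.

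3. The low figures combine the smallest enrolment, the lowest forecast engagement and no background use. The shortfall does depend on these inputs, and 40% engagement removes it. But 30% and 50% are the Power paragraph's own inputs, and adding 2% background use still leaves one-arm and four-arm power below 80% at the floor.

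4. The exact 69% falls at a dip caused by discreteness; at 49 per arm it is 73%. Both are below 80%.

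5. This is a small-scale feasibility experiment, and the plan expects extra power from the complier analysis. The first limits the consequence. The second does not settle it, because the 80% is stated for ITT and ITT is the fallback if the instrument is weak or its assumptions fail.

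**Conclusion.** The concern holds. The 80% is right at 70 per arm, but no section aims for that size, and at the permitted floor the plan's own inputs give 65% (exact 69%) for each arm against comparison and 60% for a four-arm test. For pooled encouragement against comparison the floor gives 78% (exact 83%), so there is little or no shortfall if that is the primary contrast. The figures rest on 2% versus 15% use and on the assumptions listed with the inputs. This should be corrected, but it does not undermine the design: enrolment may well exceed the floor, and the trial is mainly about feasibility.

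**What to change.** Restate the Power paragraph over the enrolment the plan allows, on one scale, and name the contrast. Suggested text:

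> For any My HealtheVet use of 2% versus 15%, two-sided alpha 0.05 and equal allocation, power of the uncorrected chi-square test (exact or simulated) at 50, 70 and 75 per arm is about 69%, 85% and 88% for each encouragement arm versus comparison, 60%, 81% and 85% for the four-arm test, and 83%, 95% and 96% for pooled encouragement versus comparison. These figures assume 30% engagement and no use among non-engagers. At 50 per arm, power for one arm versus comparison is 76% with 2% background use and 89% with 40% engagement. The primary ITT contrast is [sponsor to state].

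If the sponsor keeps the normal approximation, the corresponding figures are 65%, 79% and 82% for one arm, 78%, 93% and 94% pooled, and 71% and 83% for the two sensitivities. The four-arm figures are simulated and should be labelled so if they are shown beside these. Once the contrast is chosen, the lines for the others can be dropped.

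The choice of contrast is the sponsor's. The cost is a rewritten paragraph, with no added participants or mailings; the one drawback is that arm-level and four-arm power at the lower end of enrolment will look less favourable than 80%. The March 2020 modifications in Section 4 show that training invitations had already gone out, so the contrast should be fixed before outcome data are analysed.
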